13.5 Secondary outcome summaries and model Estimates

Table 9: Summaries*# and Model results

	CBA N =	PEP N=	Usual Care N =	Effect sizeª	95% CI	p- value	Effect size ^b	95% CI	p- value
BRAF-MDQ (fati	gue) *c								
Baseline									
10wks									
28wks									
56wks (p)									
HADS *c									
Anxiety									
Baseline									
10wks									
28wks									
56wks (^p)									
Depression									
Baseline									
10wks									
28wks									
56wks (^p)									
Short Form-12 *	2								
SF-12 PCS									
Baseline									
10wks									
28wks									
56wks (^p)									
SF-12 MCS									
Baseline									
10wks									
28wks									
56wks (p)									
Pain numerical r	ating scale	*c							
Baseline									
10wks									
28wks									
56wks (p)									
Sleep problem so	ale *c								
Baseline									
10wks									
28wks									

SAP version 1: LIFT

56wks (p)									
WPAI*c for all 4 domains									
Baseline									
10wks									
28wks									
56wks (p)									
Valued Life Activ	vities Scale	(short 14 iter	ms) *c						
Baseline									
10wks									
28wks									
56wks (p)									
Global Outcome	e								
10wks									
28wks									
56wks (^p)									

All models adjusted for their baseline outcome measure where appropriate (not Global outcome), HADS depression subscale >10 at baseline as fixed effects fixed effect with Centre clustering and individuals nested within centres as random effects

*Treated as Continuous data: n; mean (sd), median (IQR) and (min, max)

Binary x/n (%)

^a Mean difference between CBA and Usual care

 $^{\rm b}$ Mean difference between PEP $\,$ and Usual care

^cMultilevel mixed-effects generalized linear model (glm) accounting for different time points.

^e Multilevel mixed-effects glm ordinal regression and robust variance – (ref Zou 21004 (5), accounting for time points as interaction terms

^p Primary time point

13.6 Mediation and Moderation analyses

Table 10: TBC by [name] as secondary analyses

13.7 Quantitative evaluation

Table 11:

Actual allocation	CBA N =	PEP N=	Usual Care N =	Effect sizeª	95% CI	p- value	Effect size ^b	95% CI	p- value
Patient preference	e for treatr	nent options	#a						
CBA									
PEP									
Usual Care									
Patient Acceptability Score*									

Binary x/n (%) those who got their preferred treatment

^a Mixed-effects glm as a Modified Poisson Regression with log link and robust variance –(ref Zou) adjusted for HADS depression subscale >10 at baseline as fixed effects fixed effect with Centre clustering and individuals nested within centres as random effects

* Additional adjusting variable as a sensitivity analysis

Recall:

The main analysis to assess preference on the treatment effect whereby 'no preference' will be considered as being 'not matched' ie did not get their preferred treatment.

Two sensitivity analyses will be considered regarding those who 'had no preference'.

- To drop them from the analysis
- To include in the 'matched' group.

Another set of sensitivity analyses will assess the impact of adjusting for 'how positive' participants were about receiving their preferred option.

14 References

- 3. Sean Grant, Evan Mayo-Wilson, Paul Montgomery, Geraldine Macdonald, Susan Michie, Sally Hopewell, David Moher, on behalf of the CONSORT-SPI Group 'CONSORT-SPI 2018 Explanation and Elaboration: guidance for reporting social and psychological intervention trials' *Trials* (2018) 19:406
- 4. G Dunn, R. A. Emsley, H Liu, S Landau, J Green, I White, and A Pickles. Evaluation and validation of social and psychological markers in randomised trials of complex interventions in mental health. Health Technology Assessment, 19(93), 2015.
- 5. Zou G. A Modified Poisson Regression Approach to Prospective Studies with Binary Data. Am J Epidemiol 2004;**159**:702–6. https://doi.org/10.1093/aje/kwh090.
- 6. J Nicklin, F Cramp, J Kirwan, R Greenwood, M Urban, S Hewlett. Measuring fatigue in rheumatoid arthritis: a cross-sectional study to evaluate the Bristol Rheumatoid Arthritis Fatigue Multi-Dimensional questionnaire, visual analog scales, and numerical rating scales. Arthritis Care Res (Hoboken). 62 (2010) 1559-1568.

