# 3.4 Quantitative process evaluation

#### 3.4.1 Patient preference

Participants will be given short synopsis of all three treatments, usual care, CBA and PEP interventions as treatment for IRD-related fatigue. They will then be asked about which treatment they would choose if they had a choice, as well as about their strength of preference.

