# 3.4.2 Patient adherence and acceptability

Patient adherence to the interventions will be monitored via attendance records kept by the therapists. In addition, participants receiving the CBA or PEP interventions will be contacted by telephone interview by member of trial office Aberdeen at time of session 4 (approximately week 8) and session 8 (approximately week 26). They will be asked to indicate on a scale from 0 (not at all) to 10 (completely), if they think that this treatment is the right approach and their willingness to engage and adhere to the intervention. At the same time, the therapists will be asked during supervision to what extent they think that the participant has engaged with treatment and adhered to the agreed actions and

plans. Intervention acceptance by participants will be evaluated in all three treatment arms using the Client Satisfaction Questionnaire [44] at 28 weeks.

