6.4 Quantitative evaluation (Qualitative evaluation not covered here)

- Patient preference (only at baseline)
- Patient acceptability (assessed at week 28)

	ning	Proposed assessment [wks]			
	Scree	0	10	28	56
Demographic data					
Date of birth, gender, marital status, employment		~			
status, level of education					
Characteristics of study generalation					
Characteristics of study population					
Overall health (from domain in SF-12)		√			
Physical activity (typical self-reported)		√			
Experience of fatigue for more than 3 months	✓	✓			
Average level of fatigue(self reported- scale 1-10)	\checkmark	\checkmark			
Thyroid function test		\checkmark			
Urea and electrolytes		\checkmark			
Full blood count		✓			
Serological status ^s		\checkmark			
Erosive status		\checkmark			
Disease duration		\checkmark			
Presence of other co-morbidities		\checkmark	\checkmark	\checkmark	✓
(Charlson Index) ^D					
History of Suicide attempts		\checkmark			
Disease activity DAS28, ASDAS and BILAG for RA,		\checkmark	\checkmark	\checkmark	\checkmark
AxSpA and SLE respectively ^S					
Inflammation (CRP/ESR)		\checkmark	✓	✓	✓
Previous and current pharmacological therapies		\checkmark	\checkmark	\checkmark	\checkmark
Hypertension / Blood pressure ^S		\checkmark			

7 Timing of Outcome Measures

Primary Outcome					
Chalder Fatigue Scale (Likert scoring) D	~		✓	~	✓
Fatigue Severity Scale (FSS) D	~	1	\checkmark	\checkmark	\checkmark
Secondary Outcomes					
BRAF-MDQ (fatigue)	~	, ,	✓	✓	√
HADS (anxiety and depression)	~		√	✓	✓
Short Form-12 ^D	~		✓	✓	✓
Pain numerical rating scale ^D	~		✓	✓	✓
Sleep problem scale	•	/	\checkmark	\checkmark	\checkmark
Work Productivity and Activity Impairment	· ·	/	\checkmark	\checkmark	\checkmark
Questionnaire ^D					
Valued Life Activities Scale (short 14 items) D	~	/	\checkmark	\checkmark	\checkmark
Global outcome ^D			\checkmark	\checkmark	\checkmark
Additional mediator/moderator data					
Cognitions and behaviours		_			
Brief Illness Perception Questionnaire D	~		✓	✓	✓
Behavioural Response to Illness Questionnaire D	~	_	✓	\checkmark	✓
Clinical					
Procence of fibromyalgia D		/			✓
Disease estivity (self reported)		/	1	√	• •
Disease activity (self-reported)	· ·	_	•	•	v
Physical					
Physical activity profiles, over a 7 day period \$	•	/	\checkmark	\checkmark	\checkmark
Quantifying aerobic fitness (step) test (weight, VO ₂	~	/	\checkmark	\checkmark	\checkmark
max and Borg Rating of Perceived Exertion) \$					

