11.4 Quantitative evaluation Analysis

The main analysis to assess preference on the treatment effect whereby 'no preference' will be considered as being 'not matched' i.e. did not get their preferred treatment.

Two sensitivity analyses will be considered regarding those who 'had no preference'.

- To drop them from the analysis
- To include in the 'matched' group.

Another set of sensitivity analyses will assess the impact of adjusting for 'how positive' participants were about receiving their preferred option, summarised in the table see dummy tables below*. *post randomisation moderator effects such as therapist/HCP effect analyses, patient adherence will be a secondary analysis phase.*

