Recommend this program to a friend? 1:No, definitely not; 2:No, I don't think so;		
3:Yes, I think so; 4:Yes, definitely; 99:Not answered;		
Satisfied with the amount of help received? 1:Quite dissatisfied; 2:Indifferent or mildly dissatisfied; 3:Mostly satisfied; 4:Very satisfied; 00:Net answered;		
 Have the services received helped to deal more effectively with problems? 1:Yes, they helped a great deal; 2:Yes, they helped; 3:No, they really didn't help; 4:No, they seemed to make things worse; 99:Not answered; 		
How satisfied with the service received overall? 1:Very satisfied; 2:Mostly satisfied; 3:Indifferent or mildly dissatisfied; 4:Quite dissatisfied; 99:Not answered;		
Would you come back to this program if needed? 1:No, definitely not; 2:No, I don't think so; 3:Yes, I think so; 4:Yes, definitely; 99:Not answered:		

*Continuous data n; mean (sd), median (IQR) and (min, max)

‡ Summary of Item 1-8 plus overall Score. Also Item 9 indicates causality, BUT will need to be coded and analysed separately (text data) SG : TBC by [name]

† Patent engagement & adherence (therapist view) at 8 weeks forms the CACE variable (if missing the 4 week) reported value to be substituted

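### SAP Table 11 marks the 28-week Patient Acceptability Score as the adjusting variable for a preference sensitivity analysis, while section 11.4 describes a different variable

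*SAP*

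**What the plan says.** Table 11 (SAP 13.7) has a row labelled "Patient Acceptability Score" that carries an asterisk. The legend of that table gives the asterisk its own meaning: "Additional adjusting variable as a sensitivity analysis". In the other dummy tables an asterisk denotes continuous data.

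The timing of the score is clear. SAP 6.4 lists "Patient acceptability (assessed at week 28", and protocol 3.4.2 states: "Intervention acceptance by participants will be evaluated in all three treatment arms using the Client Satisfaction Questionnaire [44] at 28 weeks". The items appear in SAP Tables 5a-d and ask about the service received, for example "Have the services received helped to deal more effectively with problems".

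SAP 11.4 defines the main preference analysis without acceptability: "The main analysis to assess preference on the treatment effect whereby 'no preference' will be considered as being 'not matched". Two sensitivity analyses vary the handling of participants with no preference. Then comes the relevant sentence: "Another set of sensitivity analyses will assess the impact of adjusting for 'how positive' participants were about receiving their preferred option". It sends the reader to the dummy tables, and the reminder under Table 11 repeats it.

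Protocol 3.4.1 records which treatment participants would choose, "as well as about their strength of preference". The study matrix (protocol 3.8) counts two preference items, both at baseline only.

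**The concern.** An analyst who follows 11.4 to the dummy tables finds one variable marked for adjustment in Table 11, and it is measured after treatment has begun. Satisfaction at 28 weeks can depend on the arm received, on whether that arm was the preferred one, and on how much the participant has improved so far. A model containing it no longer estimates the total effect of arm or of matching. It can also open a non-causal path through any unmeasured factor that drives both satisfaction and fatigue. The model is further limited to people who completed the 28-week questionnaire, which is itself a selection after randomisation.

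A sensitivity analysis is meant to show whether a result is robust. Here a change in the estimate could come entirely from the adjustment, yet be reported as evidence that the preference finding is fragile.

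**Working it through.** No figure in the plan bears on this point, and the sample size (100 evaluable, 125 recruited per group) is unaffected. The check is mainly a comparison of texts.

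1. **Which variable is marked?** Table 11 marks the acceptability score. The asterisk's meaning comes from that table's legend, so it cannot be read as the continuous-data marker used elsewhere.
2. **When is it measured?** At week 28, in all three arms (SAP 6.4, protocol 3.4.2). It is post-randomisation.
3. **What does it measure?** Reaction to the service received, including perceived benefit (items in Tables 5a-d). It can respond to both arm and match.
4. **What does the text ask for?** Adjustment for how positive participants were about getting their preferred option (11.4 and the reminder under Table 11). No instrument is named.
5. **Is there a baseline candidate?** Yes, strength of preference (protocol 3.4.1). The SAP never names it; its appendix describes patient preference as a single item, whereas the protocol matrix counts two.
6. **What does the SAP do with other post-randomisation variables?** 11.4 defers post-randomisation moderator effects to a secondary phase, giving therapist effects and adherence as examples. Acceptability is not listed.

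**Illustration of the mechanism. All satisfaction, preference and match values are assumed.** Section 11.4 does not name the outcome for the preference analysis, so take CF with the SAP's SD of 4. Let δ be the shift in acceptability (in SD units) caused by receiving the preferred treatment, and ρ the size of the correlation between acceptability and CF, given arm, preference and match, through a shared unmeasured cause, with more satisfied people less fatigued. In a linear model:

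absorbed part of the match effect = δ × ρ × 4

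| δ | ρ | Absorbed | Left of an assumed 1-unit match effect |
|---|---|---|---|
| 0.3 | 0.15 | 0.3 × 0.15 × 4 = 0.18 | 0.82 |
| 0.3 | 0.25 | 0.3 × 0.25 × 4 = 0.30 | 0.70 |
| 0.5 | 0.25 | 0.5 × 0.25 × 4 = 0.50 | 0.50 |
| 0.5 | 0.35 | 0.5 × 0.35 × 4 = 0.70 | 0.30 |

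A large-sample simulation under the same assumptions gave 0.84, 0.70, 0.50 and 0.29. Without acceptability in the model it recovered the assumed effect of about 1. If δ = 0 or ρ = 0, this bias in the match effect is zero. If the correlation had the opposite sign, so would the bias.

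**Table 11 taken literally.** The footnoted model is a log-link modified Poisson regression for whether participants got their preferred treatment. Suppose 35% prefer CBA and 10% prefer usual care. The CBA to usual care ratio is then 0.35 / 0.10 = 3.5. In the simulation, adding acceptability moved it to 3.04–3.11 when arm and match shift satisfaction by 0.5 and 0.3 SD, and to 2.55–2.65 when the shifts are 0.8 and 0.5 SD. It did not move when neither arm nor match affected satisfaction. The outcome is settled at allocation, so a 28-week score cannot be on its causal pathway. The ratio moves only because the model conditions on a later consequence.

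**The case against.** The strongest reply is that the documents show no settled decision to adjust for satisfaction. Both 11.4 and the reminder directly under Table 11 describe a different variable, and 11.4 defers post-randomisation moderators. The acceptability row also has arm and effect-size columns, so it could be an outcome row to which an extra adjuster is added. On this view the asterisk is a slip in a table shell. That is plausible, and it is why the point is best put as a conflict to reconcile. It does not remove the point: the legend is explicit, the text names no instrument, and the text sends the analyst to the tables.

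A reader might infer that the trial's treatment effect is at risk. The documents do not support this. The covariates listed for the primary CF and FSS models (SAP 11.2 and the Table 8 notes) do not include acceptability, and neither the main preference analysis nor the two no-preference variants use it. Setting an absorbed amount against the 2-unit target in SAP section 10 would borrow a quantity from an analysis that is never adjusted this way; Table 11's footnoted model is not in CF units at all.

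A reader might also infer that 11.4 clearly means the baseline strength-of-preference item. That is the likely reading, but neither document says so.

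**Conclusion.** Wrong as written, and limited to one sensitivity adjustment. Table 11 names a 28-week response to treatment as the additional covariate, in conflict with 11.4 and with the reminder below the table. If the table is followed, the adjusted sensitivity estimate would generally be biased and could be misread as instability of the preference result.

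The documents give no satisfaction data, so neither the size nor the direction of the bias can be derived from them; the worked values show the mechanism only. The conclusion rests on acceptability being affected by arm or match and being related to the outcome analysed. Given what the questionnaire asks, both are plausible. The main preference analysis and the primary analyses stand as planned.

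**What to change.** Reconcile Table 11 with SAP 11.4:

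- Remove the adjusting-variable asterisk from the acceptability row of Table 11.
- In 11.4 and the Table 11 legend, name the baseline strength-of-preference item (protocol 3.4.1, the second of the two preference items in the study matrix) as the additional covariate. The SAP authors should confirm that this is what 11.4 means.
- Add it to the existing adjustment for HADS depression and centre; it does not replace them.
- Correct the SAP appendix entry that treats patient preference as a single item.
- Keep acceptability as a 28-week summary by arm, which Tables 5a-d already provide.
- If adjustment for acceptability is really intended, move it to the secondary phase with mediation-type methods, and do not present the result as a robustness check.

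The cost is SAP wording only. The baseline item is already in the protocol's data collection, and neither the sample size nor any primary analysis changes.

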Presence of	Minimal missing data as completed by RN	Remains missing
fibromyalgia	Continuous analysis and dichotomous. Made	if any missing
	up of 2 subscales combined	
Disease activity	Minimal missing data as completed by RN	Remains missing
(self-reported)	during visit	
Disease activity	Minimal missing data as completed by RN	Remains missing
DAS28 for RA	during visit, except remote visits	
ASDAS	Minimal missing data as completed by RN	Remains missing
	during visit, except remote visits as not CRP	
	sample taken	
BILAG	Completeness depending on medical notes	Remains missing

Quantitative evaluation

Item	Rational	MV Decision
Patient preference	Single item	See left
	 Missing, set to "no stated preference" 	
	• 2 options ticked, set to "no stated preference"	
Patient adherence	Data derived from therapist notes if sessions	Remains missing
	took place (attendance records)	
PEA -phone	Single item	Remains missing
sessions 4 & 8		
PEA - therapist	Single item	Remains missing
sessions 4 & 8		

PEA: Patient engagement & adherence; PAct: Patient acceptability

20% rule: for each sub scale use person specific mean imputation if <= 20% items are missing
